	
for 21 days in a 28 day cycle X 2 cycles or until terminating event occurs;
 
 In subjects receiving lenalidomide, the CD34+ donor chimerism will be performed at Days +60 and +120 (± 7 days) of lenalidomide therapy.
Safety Assessments:	
Subjects will be examined weekly per institutional standard of care. Examinations will consist of vital sign measurements, physical examinations, laboratory assessments (hematology, serum chemistries) and assessment of acute GVHD. NCI Common Terminology Criteria for Adverse Events (CTCAE), Version 4.0 will be used to grade toxicity and adverse events.
 
GVHD assessment: Acute GVHD will be evaluated as per institutional practice guidelines using established staging criteria (see Appendix F). GVHD severity will be determined clinically; however, biopsies of affected organs are encouraged whenever possible. GVHD assessments will be performed at screening and Days +60 & +90. If lenalidomide is initiated, GVHD assessments will be performed weekly during scheduled visits and continuing until 30 days after the last dose of lenalidomide. GVHD assessments will also be documented at Days +60 and Day +120 after the initiation of lenalidomide.
 
Overall grading and response to GVHD therapy will be measured through the use of the consensus and IBMTR GVHD severity indices based on physical exam and laboratory serum values (see Appendix F). Individual organ stages will be scored by the attending physician or other trained provider.

Immunosuppression:	All patients should receive standard GVHD prophylaxis per institutional guidelines per the treating physician.
Efficacy Assessments:	The efficacy outcome of interest will be reversal of the decreased CD34+ specific donor chimerism by day 60 of lenalidomide administration.

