Statistical Procedures:	This study is descriptive in nature and not designed to provide analytical inferential results regarding primary or secondary endpoints. The sample size is based primarily on clinical considerations and not on statistical power calculations. Statistical characteristics of the “3 + 3” design are described in Appendix G. Descriptive statistics will be used to summarize baseline subject characteristics, treatment administration, and safety variables. All subjects who receive at least 5 doses of lenalidomide and have one post-dose safety assessment will comprise the safety population. The efficacy evaluable population will comprise all subjects who complete

	at least 15 days of lenalidomide and have at least one post-therapy CD34+ specific chimerism assessment.
--	--

Schedule of Events

Assessment	Screening (+/-7 days from Day +60)	Post- Transplant Monitoring Days +60 & 90 (\pm 7 days)	Revlimid C1D1, C2D1	End of Treatment 30 Days post- last Revlimid Dose (\pm 2 days)	Post- Revlimid Monitoring Days +60 & +120 (\pm 7 days)	Survival Every 3-months for 1 year
Signed Informed Consent	X					
Demographics, Medical /Treatment History	X					
MDS and AML WHO Classification	X					
Weight, Height	X					
Physical Examination	X	X	X	X	X	
GVHD Assessment ^A	X	X	X	X	X	
Vital Signs	X	X	X	X	X	
Karnofsky Performance Score	X	X	X	X	X	
CBC + Differential	X	X	X	X	X	
Serum Chemistry	X	X	X	X	X	
Serum Pregnancy Test (females) ^B	X		X			
Bone Marrow Aspiration and Biopsy ^C	X					
Peripheral Blood Chimerism		X				
Peripheral blood CD34+ donor chimerism ^D		X			X	
Dispense Revlimid (21-day supply)			X			
Concomitant Medications	X	X	X	X		
Adverse Events Assessments	X	X	X	X		
Concomitant Blood Products	X	X	X	X		
Disease Response Assessment ^C	X	X				X
Survival Assessment				X		X

- A. Overall grading and response to GVHD therapy will be measured through the use of the consensus and IBMTR GVHD severity indices. GVHD assessments will be performed at screening and Days +60 & +90. If lenalidomide is initiated, GVHD assessments will be performed weekly during scheduled visits and continuing until 30 days after the last dose of lenalidomide. GVHD assessments will also be documented at Days +60, and Day +120 after the initiation of lenalidomide.

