- B. Females of reproductive potential must have 2 negative pregnancy tests prior to initiating therapy. The first test should be performed within 10-14 days, and the second test within 24 hours prior to prescribing REVLIMID therapy and then weekly during the first month, then monthly thereafter in women with regular menstrual cycles or every 2 weeks in women with irregular menstrual cycles.
- C. All disease assessments which occur during routine care of the subject will be recorded in the CRF. Bone marrow procedures or other disease assessments will be performed according to institutional guidelines or physician discretion.
- D. The peripheral blood CD34+ donor chimerism will be performed on days +60 and +90 (\pm 7 days) post-transplant until the CD34+ donor chimerism drops to \leq 90%. In subjects receiving lenalidomide, the CD34+ donor chimerism will be performed at Days +60 and +120 (\pm 7 days) of lenalidomide therapy. Additional CD34+ donor chimerism testing will be performed at the discretion of the clinical investigator (e.g., when a subject develops peripheral blasts, worsening pancytopenia, or extramedullary relapse).

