11. DISCONTINUATIONS

11.1 Discontinuation of Subjects

A subject must be discontinued from protocol-prescribed therapy under the following circumstances:

- Consent withdrawal at the subject's own request or at the request of their legally authorized representative;
- Unacceptable toxicity or adverse event as determined by the Principal Investigator and/or subject;
- Significant deviation from inclusion/exclusion criteria, in the opinion of the Principal Investigator;
- If, in the Principal Investigator's opinion, continuation in the study could be detrimental to the subject's well-being;
- Relapsed or progressive disease;
- Initiation of chemotherapy for relapsed or progressive disease.

If a female subject or the female partner of a male subject who is required to use defined contraceptive methods becomes pregnant after the study, the female subject or pregnant partner must be followed until the outcome of the pregnancy is known.

As far as possible, all end-of-study examinations must be performed on all subjects who receive the study drug but do not complete the study according to protocol. All subjects who discontinue from protocol-prescribed therapy for any of the reasons above will be followed for a period of 30 days following the last day of study drug administration.

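### Disease status is not a scheduled entry at the on-drug and chimerism visits, and no rule says how relapse, death or new anti-cancer therapy before the chimerism sample is scored

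*Combined protocol and SAP*

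**What the plan says.** All references are to the combined protocol and SAP.

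- **Schedule of Events.** The row "Disease Response Assessment" is ticked at Screening, at Post-Transplant Monitoring (Days +60 and +90) and in the 3-monthly Survival column. It is blank at C1D1/C2D1, End of Treatment and Post-Revlimid Days +60 and +120. Marrow examination is ticked at Screening only.
- **Footnote C.** It has two sentences. The first covers capture: "All disease assessments which occur during routine care of the subject will be recorded in the CRF". The second covers whether an assessment takes place: "Bone marrow procedures or other disease assessments will be performed according to institutional guidelines or physician discretion".
- **Footnote D.** "In subjects receiving lenalidomide, the CD34+ donor chimerism will be performed at Days +60 and +120", with a window of ±7 days. Extra chimerism tests are discretionary; extramedullary relapse is one of the listed prompts.
- **Synopsis, Efficacy Assessments.** "The efficacy outcome of interest will be reversal of the decreased CD34+ specific donor chimerism by day 60 of lenalidomide administration". There is no relapse condition and no numeric definition of reversal.
- **Efficacy populations.** The Synopsis asks for 15 days of drug and Section 13.2.3 for 21, each with at least one assessment afterwards. Neither excludes a subject who has relapsed or started other treatment.
- **Section 13.3.2.** Frequencies and 95% confidence intervals, with no rule for intervening events.
- **Section 11.1.** "Relapsed or progressive disease" ends protocol therapy. Nothing links that event to how the endpoint is scored.

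**The concern.** The programme aims to prevent or delay haematologic relapse, and chimerism reversal is the only efficacy outcome the protocol names. A reader of the result will take a reversed subject to be one in whom lenalidomide helped. As written, a subject could take 21 days of drug, relapse, stop under Section 11.1, remain in the efficacy population and give a restored blood CD34+ donor chimerism at day 60. There are two plausible routes: extramedullary relapse, which a blood value need not show, or salvage treatment that restores donor chimerism before the sample. Nothing in the plan stops either case from being credited to lenalidomide.

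The opposite problem also exists. Both populations require a post-treatment assessment, so a subject who dies before any sample drops out of the denominator instead of counting as a failure.

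At stake is how the activity signal taken into the planned phase II trial is read. Dose escalation is not at stake.

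**Working it through.** The plan gives no figure for this point, so there is none to reproduce. The check covers visit timing and then the effect of one subject.

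**1. Visit timing (first dose = day 1; two 28-day cycles, dosing on days 1–21 of each)**

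- C2D1: day 29. Last scheduled dose: 28 + 21 = day 49.
- End of Treatment: 49 + 30 ± 2 = days 77–81.
- Chimerism windows: 60 ± 7 = days 53–67, and 120 ± 7 = days 113–127.

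**2. Where the ticked disease assessments can fall**

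- *Post-transplant Day +90.* A subject triggered at post-transplant Day +60 ± 7 (transplant days 53–67) starts within 10 days, so on transplant days 53–77. The Day +90 visit is on transplant days 83–97. In treatment days it falls between 83 − 77 + 1 = 7 and 97 − 53 + 1 = 45, if it is still carried out. That is after first dose but before the day-60 window opens on day 53.
- *3-monthly contacts.* No anchor is stated. Taking three months as 91 days, the first falls on 1 + 91 = day 92 (from first dose), 49 + 91 = day 140 (from last dose) or 79 + 91 = day 170 (from End of Treatment). All are after day 67, the close of the day-60 window.

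So no scheduled disease assessment coincides with the day-60 sample on any of these readings.

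**3. Capture of new anti-cancer therapy before the sample**

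Section 7.1 records concomitant treatment until 28 days after the last dose, and that row is not ticked at the Post-Revlimid visits.

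- Stopped on day 21: recording closes on 21 + 28 = day 49, before the window opens on day 53.
- Full course: recording closes on 49 + 28 = day 77. That covers the day-60 sample but not the Day +120 sample.

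**4. Effect of one subject scored the other way**

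One subject is worth 1/n: 1/3 = 33 points, 1/6 = 17 points, 1/24 = 4 points. The exact (Clopper–Pearson) limits are the 0.025 quantile of Beta(x, n − x + 1) and the 0.975 quantile of Beta(x + 1, n − x). The counts are illustrative; 24 is the maximum sample size in Section 13.1, with all taken as evaluable.

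| n | Relapsed subject counted as reversed | Counted as not reversed |
|---|---|---|
| 6 | 2/6 = 33% (4–78%) | 1/6 = 17% (0.4–64%) |
| 24 | 8/24 = 33% (16–55%) | 7/24 = 29% (13–51%) |

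**5. How often this might happen**

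The documents give no rate. In the Synopsis pilot data, 4 of 10 patients relapsed and all 4 had a fall in CD34+ chimerism first, so 0 of 4 were discordant. That points to an uncommon event. Four cases cannot rule it out: the exact 95% upper limit for 0/4 is 1 − 0.025^(1/4) = 0.60.

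**The case against.** The strongest reply is that surveillance is not missing. Subjects are examined weekly. Section 9.2.2.2 sets weekly haematology on lenalidomide and for 3 weeks afterwards. Examination and CBC with differential are ticked at every visit in question. Worsening of the treated condition is an adverse event (Section 10.1.1), and adverse events are documented once drug starts (Section 10.3). Footnote C sends routine disease assessments to the CRF. This stands: much overt relapse will be seen and recorded. What is missing is a systematic disease-status entry at the endpoint and a rule for using it.

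It can also be said that Section 3.2 asks only for monitoring of chimerism, so a chimerism-only summary meets the objective. That is fair, and is why that summary should be kept beside the other.

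Three stronger readings are tempting, and the documents do not support them:

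- *That no disease assessment occurs between first dose and Day +120.* The post-transplant Day +90 assessment can fall on treatment, and a 3-monthly contact anchored at first dose would fall near day 92.
- *That the protocol counts any value above the 90% trigger as reversed.* It defines no threshold for reversal. That omission is a separate matter.
- *That the reversal proportion is inflated by a calculable amount.* No rate of relapse with restored chimerism is given. The pilot's 4 in 10 has no stated follow-up time, so it cannot serve as relapse by day 60.

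**Conclusion.** The concern holds in limited form. Disease status is not a scheduled entry at C2D1, End of Treatment or Post-Revlimid Days +60 and +120, and nothing says how relapse, death or new anti-cancer therapy before the chimerism sample is scored. A relapsed or salvage-treated subject with a restored value is thus not prevented from counting as a success.

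Such a case is probably uncommon on the pilot evidence. The size given is the effect of a single subject: 17 to 33 points in a cohort of 6 or 3, and about 4 points in 24. It rests on illustrative counts and full evaluability and is not an estimate of bias. The intervals overlap almost entirely, so the point concerns what a success means more than precision.

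The endpoint is secondary and descriptive, no dose decision uses it, and the MTD is unaffected. This is a cheap improvement. Settling the rule beforehand avoids case-by-case adjudication in a small open-label trial.

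**What to change.** 1. **Schedule of Events.** Tick the disease response row at C2D1, End of Treatment and Post-Revlimid Days +60 and +120. Base the entry on the examination and CBC with differential already done there, plus any routine marrow result; no procedure is added. Record new anti-cancer therapy up to the date of the chimerism sample, and state the date from which the 3-monthly contacts are counted.
2. **Synopsis and Section 13.3.2.** Count a subject with relapse (haematologic or extramedullary), death or new anti-cancer therapy on or before the sample date as not reversed, and report the chimerism-only proportion beside it. For deaths to count, Section 13.2.3 must keep in the denominator subjects who meet the exposure threshold but have one of these events before a sample is taken. The 15-day and 21-day thresholds should be reconciled in the same edit.

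The cost is one CRF entry per existing visit, a few sentences of text, and possibly a slightly lower reversal proportion. Treatment and clinical management are unchanged.

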1. BACKGROUND

This clinical trial provides an investigational therapeutic option to prevent disease relapse in patients with high risk AML and MDS after allo-HCT.

1.1 Acute Myelogenous Leukemia

Acute myelogenous leukemia (AML) is a hematologic malignancy arising from a clonal hematopoietic stem cell and characterized by accumulation of malignant myeloblasts in the bone marrow and resulting in ineffective hematopoiesis. AML is the most common type of acute leukemia in adults in the United States, with over 11,000 new cases reported each year.¹ It is widely known that AML remits initially to conventional cytotoxic chemotherapy, but often relapses due to (1) genetic and epigenetic abnormalities conferring insensitivity to conventional cytotoxic agents, and (2) protective microenvironments that support leukemia cell survival and proliferation.^{2,3} Whereas initial remission rates are 50-80%, long-term disease-free survival is 20% in patients achieving a complete remission and less than 10% overall.¹ Relapsed and refractory disease are major challenges.

The prognosis for patients with AML relapsing after allo-HCT is very poor. The duration of first remission in relapsed patients is the most important prognostic factor correlating with the probability of second CR and survival.⁴ Patients with primary refractory and early relapsed disease with a CR duration < 6 months have a significantly poorer response to therapy and OS than do patients who relapsed after a first CR lasting \geq 6 months (CR rate 10%–30% vs. 40%–60%, respectively).⁵⁻⁸ The optimum strategy at the time of relapse for patients with resistant disease remains uncertain.

1.2 Myelodysplastic Syndromes

The myelodysplastic syndromes (MDS) are a heterogeneous group of clonal neoplastic hematopoietic stem cell disorders. They are characterized by a hypercellular bone marrow, with dysplastic ineffective hematopoiesis resulting in peripheral blood cytopenias. MDS most often affects elderly people. The incidence of MDS is 50 per 100,000 in the population over age of 60, and it is the most common hematological malignancy in this age group.⁹ Thirty to fifty percent of cases of MDS eventually evolve into AML, therefore this syndrome historically has been called oligoblastic leukemia, smoldering acute leukemia, or preleukemia.¹⁰

The decision to treat MDS is generally based on age of the patient, performance status, and International Prognostic Scoring System (IPSS) score.¹¹⁻¹³ While some patients with low risk disease and stable blood counts do not need immediate treatment and can be followed without therapy, others with Low and Intermediate-1 risk IPSS scores may require treatment to alleviate cytopenias and improve quality of life. Such patients are usually treated with low intensity approaches such as supportive care, including antibiotics, blood product transfusion, hematopoietic growth factors, immunosuppressants, immunomodulators, and inhibitors of angiogenesis. Epigenetic modulators, farnesyltransferase and tyrosine kinase inhibitors target molecular aberrations seen in later stages of MDS. Higher intensity therapies which aim at changing the natural history of disease are usually reserved for patients with excess myeloblasts (RAEB-1 and RAEB-2 disease) and Intermediate-2 and High risk IPSS scores.

Despite significant progress in treatment of advanced disease MDS (RAEB-1, RAEB-2, Intermediate-2 IPSS, High IPSS), the only curative therapy is allogeneic hematopoietic cell transplant, which is risky.¹⁴⁻¹⁹ In addition, few MDS patients are eligible for transplant due to co-morbidities and lack of suitable donors. Standard induction therapy for patients with advanced MDS include azanucleosides such as azacitidine (Vidaza[®]) and decitabine (Dacogen[®]), which exhibit dual properties as pyrimidine analogues and hypomethylating agents.^{20,21} These agents change the natural history of MDS, reduce transfusion requirements, extend survival, and delay progression to acute leukemia.^{20,22-25} However, only 20% of patients achieve complete and partial bone marrow remissions (CR+PR) and only 50% of patients achieve hematologic improvements. Moreover, in spite of any improvement nearly all MDS patients suffer from disease relapse and progression.

Treatment for relapsed MDS after allo-HCT is poor. There is no standard therapy. Most patients are referred to clinical trials for investigational therapy.¹³ If no clinical trial is available, best supportive care and hospice services are recommended.

1.3 Experience with Revlimid after allo-HCT in patients with Multiple Myeloma

There is a limited amount of published data available about the feasibility of lenalidomide administration after allo-HCT in patients with multiple myeloma.

Coman et al. showed that administration of lenalidomide at 25 mg/day (alone or in combination with dexamethasone) after allo-HSCT in patients with multiple myeloma was associated with high response rate, however led to the development or worsening of aGVHD in 31% patients. Importantly development of aGVHD was significantly associated with a stronger anti-myeloma response²⁶. Alsina et al. reported similar findings demonstrating that maintenance therapy with lenalidomide in myeloma patients after allo-HSC is feasible. In this study lenalidomide was started at 10 mg/day and the doses were further escalated. The median time from allo-HSCT to lenalidomide initiation was 96 days and aGVHD developed in 37% patients with a cumulative incidence of grades III to IV aGVHD of 17%²⁷. However, Kneppers et al reported that even low doses of lenalidomide at 10 mg given for 21 days of a 28-day schedule led to relatively high rates of its discontinuation, mainly because of aGVHD, which developed in 43%²⁸.

These results demonstrated the feasibility of using the CD34+ specific chimerism analysis to monitor MRD and timely detect an imminent hematologic relapse. The CD34+ specific STR analysis is superior to conventional chimerism analysis for MRD monitoring and identification of early relapse after allo-HCT. More importantly, drop of CD34+ specific chimerism occurred significantly earlier than decrease in chimerism assessed by conventional STR-based techniques. Therefore, the use of highly sensitive and specific MRD monitoring by the CD34+ chimerism analysis **substantially increases the reliability of early MRD detection** after allo-HCT **allowing early therapeutic interventions** and is **potentially practice changing**.

2. STUDY AGENT

2.1 Lenalidomide

2.1.1 Background

Lenalidomide has both immunomodulatory and anti-angiogenic properties which could confer antitumor and antimetastatic effects. Lenalidomide has been demonstrated to possess anti-angiogenic activity through inhibition of bFGF, VEGF and TNF-alpha induced endothelial cell migration, due at least in part to inhibition of Akt phosphorylation response to bFGF.²⁹ In addition, lenalidomide has a variety of immunomodulatory effects. Lenalidomide stimulates T cell proliferation, and the production of IL-2, IL-10 and IFN-gamma, inhibits IL-1 beta and IL-6 and modulates IL-12 production.³⁰ Upregulation of T cell derived IL-2 production is achieved at least in part through increased AP-1 activity.³¹

Although the exact antitumor mechanism of action of lenalidomide is unknown, a number of mechanisms are postulated to be responsible for lenalidomide's activity against multiple myeloma. Lenalidomide has been shown to increase T cell proliferation, which leads to an increase in IL-2 and IFN-gamma secretion. The increased level of these circulating cytokines augment natural killer cell number and function, and enhance natural killer cell activity to yield an increase in multiple myeloma cell lysis.³² In addition, lenalidomide has direct activity against multiple myeloma and induces apoptosis or G1 growth arrest in multiple myeloma cell lines and in multiple myeloma cells of patients resistant to melphalan, doxorubicin and dexamethasone.³³

2.1.1.1 Indications and Usage:

Revlimid® (lenalidomide) is indicated for the treatment of patients with transfusion-dependent anemia due to Low- or Intermediate-1-risk myelodysplastic syndromes associated with a deletion 5q cytogenetic abnormality with or without additional cytogenetic abnormalities. Revlimid® is also approved in combination with dexamethasone for the treatment of patients with multiple myeloma that have received at least one prior therapy.

